Colonic permeability is measured by urinary excretion of mannitol and lactulose after oral ingestion (44). We refined a previous HPLC-tandem mass spectrometry technique (45). We validated measurement of colonic permeability after oral delivery by direct instillation of sugars into the colon (46). We have published data showing significantly increased small bowel ($P < .001$) and colonic ($P = 0.10$) permeability in IBS-D (35); and effects of dietary gluten on small bowel permeability, especially in HLA DQ2/8 +ve ($P = 0.02$) patients with non-celiac IBS-D (35). We validated ^{13}C -mannitol to avoid confounding by dietary ^{12}C -mannitol (47).

Rectosigmoid **mucosal expression of tight junction (TJ) proteins**, a measure of barrier function: IBS-D

* $P < 0.05$	Healthy (n=16)	IBS-D (n=25)
ZO-1	1.00 \pm 0.024	0.960 \pm 0.046*
Claudin	1.00 \pm 0.018	1.003 \pm 0.020
Occludin	1.00 \pm 0.016	0.931 \pm 0.025*

patients have lower mRNA expression of TJ proteins [ZO-1 and occludin (both $P < .001$)], but not claudin proteins (35) relative to healthy controls; values show fold change vs. mean in controls (Table 2).

Table 2. TJ protein expressions in rectosigmoid mucosa in IBS D and healthy controls (mean \pm SD).

In addition, gluten-containing diet was associated with

significant decreases in ZO-1 and occludin mRNA expression in rectosigmoid mucosa (48).

Mucosal morphology will assess intra-epithelial lymphocytes, mast cells and immunocytes in lamina propria, and immunohisto-chemistry of TJ proteins (35). GI pathologist will ensure correct orientation.

Colonic transit: Extensive experience over 28 years with validation of colonic transit by radioscintigraphy (49).

Gallbladder size measurement: Studies have demonstrated that patients with hormones that regulate bile acid synthesis (FGF15 in mice and FGF19 in humans) facilitate gallbladder filling. We want to determine if there is any difference of baseline and post treatment gallbladder measurements. Gallbladder measurement will be conducted fasting both pre and post treatment with a 2-D ultrasound. Patients will be in the supine position with the transducer placed in a sagittal plane in the right upper quadrant of the supine patients and positioned until the greatest length of the gallbladder is obtained. The image will be captured and the length will be measured. The probe will then be rotated 90 degrees to obtain the short axis and obtain the greatest dimension in that window.

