Human subjects and design: 30 IBS-D patients with BAM will be randomized (15/group) in 4-week double-blind, parallel-group trial to Colesevelam, 1.875g b.i.d. or placebo. Patients will be stratified on gender and BMI; we anticipate 90% female and 75% BMI >30kg/m².

[figure not shown]
Experimental procedures: Effects of colesevelam/placebo on symptoms (daily stool diaries), as well as colonic transit, fecal bile acid and fat excretion and fasting serum C4 and FGF-19, intestinal permeability and TJ expression in rectosigmoid mucosal biopsies at baseline and at end of 28 days' treatment.

Primary endpoints: 1. Bowel movements/week; 2. Stool consistency based on Bristol Stool Form Scale, BSFS.

Secondary endpoints: 1. Quantitative total fecal BAs; 2. Proportion of secretory BA (CDCA, DCA) in stool; 3.

Fasting serum C4 and FGF-19 levels; 4. Colonic transit, geometric center at 24 and 48 hours; 5. Intestinal and colonic permeability (mannitol, lactulose excretion); 6. TJ expression in rectosigmoid mucosa.

Colesevelam Study Design

This study consists of ten visits to Mayo Clinic at the Charlton 7 Clinical Research Trials Unit (CRTU). Some of the visits can be combined.

Visit 1 (Screen visit) Volunteers will be asked to come to the Charlton 7 to review and sign this informed consent form and all have all their questions answered. This visit will require about 90 minutes.

- **QUESTIONNAIRES:** Volunteers will be asked to complete two questionnaires.
 1. Bowel Disease Questionnaire, which asks questions about their bowel symptoms
 2. Hospital Anxiety and Depression Inventory, which asks about any anxiety or depression they are currently feeling
 3. Quality of Life Questionnaire, which ask you how your bowel symptoms are affecting your life
 4. Symptom Checklist, which ask you about any symptoms you are currently feeling
- **VITAL SIGNS, HEIGHT AND WEIGHT:** A nurse will take your height, weight and vital signs (pulse, blood pressure, respiration rate and temperature).
- **HISTORY AND BRIEF PHYSICAL EXAM:** A study physician will review their medical history, current medications and supplements and perform a physical exam.
- **POSSIBLE BLOOD DRAW:** A small amount of blood may be taken if the study physician determines that blood tests need to be run to see if they qualify for the study. Such as serum alphaC4 or FGF19.

If the study physician finds the volunteer eligible for the study, they will be asked to participate in the rest of the study.

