Visit 7 (24 hour image) Participants will be asked to report to the desk on Charlton 7 (fasting required) for the 24 hour image. Ultrasound measurement can be performed before or after the 24 hour image is obtained. The ultrasound gallbladder measurement should take ~ 10-15 minutes. The visit should take approximately 25 minutes.

VISITS 8 AND 9 MAY BE COMBINED

Visit 8 (48 hour image and urine collection return) Participants will be asked to report to the desk on Charlton 7 (no fasting required) to drop off their 8-24 hour urine collection and have the 48 hour image taken. The visit should take approximately 10 minutes.

Visit 9 (Flexible sigmoidoscopy) [OPTIONAL] Participants will be asked to report to the desk on Charlton 7 (no fasting required). The visit should take approximately 75 minutes.

- **ENEMA**: same as Visit 4
- **FLEXIBLE SIGMOIDOSCOPY WITH BIOPSIES**: same as Visit 4

Visit 10: End of Study:

- **DIARIES RETURN**: Participants will be asked to return the completed Treatment Bowel diary
- **MEDICATION RETURN**: On the last visit participants will be asked to return any unused medication.

Statistical analyses: Effects of treatment will be compared (using Intention-To-Treat principles) using ANCOVA with BMI, gender, baseline colonic transit and baseline fecal BA excretion as covariates.

November 1 2018: at least 75% of the participants will have completed all study procedures. We plan to complete an interim analysis in order to submit an abstract for a national gastroenterology meeting in May 2019. We anticipate completing all studies in all participants by the time the data need to be presented. At that time, we shall present the data from the ENTIRE patient cohort; that analysis will be used for the one full manuscript emanating from these data.

A senior statistician will review the interim analysis results and analyze the data related to the previously determined primary endpoints. All members of the study team and the investigative team will remain blinded to treatment arm assignment and treatment arm results until the completion of the study. Thus, this would not affect the p value when the study is completed.

Statistical power: Based on our previous open-label study, the proposed sample size (15 per group) has

Response	Mean (SD)	Detectable Δ
#Stools /week	15.1 (6.6)	7.00
Stool Form (BSFS 1-7 scale)	4.4 (1.0)	1.06
Total Fecal BA excretion μ moles/48h	3496 (2456)	2650
Fecal Fat g/24h	6.8 (3.1)	3.30
Serum C4 ng/mL	72.3 (4.3)	45

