~80% power (2-sided $\alpha=0.05$) to detect clinically relevant effect sizes in stool frequency and form (expressed as detectable difference [Δ] in 2 groups: in **Table 3: Detectable differences based on 80% power.**

Anticipated results and significance: Colesevelam will reduce stool frequency, decrease stool consistency and slow colonic transit in IBS-D with high BA

excretion.

Precautions and alternative approaches:

1. The RCT has sufficient power based on directly relevant open-label trial data with same drug and disease.
2. Other agents that reduce hepatic BA synthesis and are in development will be alternatives for BA sequestrants, e.g. FXR agonists, FGF-19 analogs.

PLANNED ENROLLMENT REPORT

Comments: 30 patients IBS-D with BAM

Racial Categories	Ethnic Categories				Total
	Not Hispanic or Latino		Hispanic or Latino		
	Female	Male	Female	Male	
American Indian / Alaska Native	1	0	0	0	1
Asian	2	1	0	0	3
Native Hawaiian or Other Pacific Islander	0	0	0	0	0
Black or African American	2	1	0	0	3
White	13	7	2	1	23
More Than One Race	0	0	0	0	0
Total	18	9	2	1	30

Inclusion of Children

Children, 18-21 years of age, and adults 21 years or older will be eligible for participation in the study as active participants or as healthy controls. However, children below 18 years of age will be excluded, since there are differences in the criteria of diagnosis in adults and children, and insufficient quantitative pediatric data on the traits to be analyzed in order to assess the phenotypes of IBS, e.g. transit, permeability, etc.

Inclusion of Women and Minorities

In advertisements for patients and healthy subjects, we shall specifically solicit participation of women and minorities. We anticipate that there will be a majority of whites and representation of blacks and Asians, consistent with the ethnic constitution of communities in southeastern Minnesota, which is approximately 90% Caucasian, 5% Southeast Asian, and 5% other minorities. The prevalence of IBS among whites, blacks and Hispanics in the U.S. is very similar.

Consideration of Sex as a Biological Variable

We plan to recruit approximately 2 females to one male patient for these studies. We shall set up special efforts to recruit males with IBS using REDCAP to identify male patients through the electronic health records

(established 17 years ago at Mayo Clinic. Thus, we have identified through search of electronic medical records that there are:

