All participants will complete the validated Bowel Disease Questionnaire [BDQ, including questions to correspond to Rome criteria (58)], the Symptom Checklist-90 [SCL-90 (59)] and the Hospital Anxiety and Depression Scale [HAD (60)]. The BDQ also includes a psychosomatic symptom checklist intended to identify somatization disorders. We have used these questionnaires extensively in several studies.

A positive diagnosis of IBS will be based on the Rome III criteria (83): At least 3 months, with onset at least 6 months previously, of recurrent abdominal pain or discomfort associated with 2 or more of the following: a) Improvement with defecation; and/or b) Onset associated with a change in frequency of stool; and/or c) Onset associated with a change in form (appearance) of stool (discomfort means an uncomfortable sensation not described as pain).

Inclusion criteria

Inclusion criteria	IBS patients
Age (yr)	18-75
Gender (F:M)	2:1
BDQ - IBS symptoms	+ve by Rome III criteria
Hospital Anxiety/Depression score	No restrictions
Abdominal surgery (except appy or choly)	None
GI medications	None past 48h

BAM

serum alpha C4 \geq 40 ng/mL or FGF19 \leq 80 pg/mL, fecal BA $>$ 2000 μ moles/48h, total fecal BA $>$ 1000 μ moles/48h + \geq 4% primary BA, or $>$ 10% primary BA

Note: If a score of \geq 11 for either anxiety or depression is obtained from the Hospital Anxiety Depression Scale, these findings will be documented in their medical record, the volunteer is informed of the findings and their primary care physician is contacted about the score. If the volunteer is experiencing active suicidal/homicidal ideations, they will be sent to the emergency room.

Exclusion criteria

In all patients diagnosed with IBS, we apply rigorous standards to exclude clinically-relevant inflammation. Patients with known bleeding diathesis will be excluded, given the need for sigmoid mucosal biopsies.

PROHIBITED MEDICATIONS

Patients participating will not take any of the following disallowed medications for at least 7 days prior to and during the remainder of the study:

1. Any treatment specifically taken for IBS-D, including loperamide, cholestyramine, alosetron
2. Drugs with a known pharmacological activity at 5-HT₄, 5-HT_{2b} or 5-HT₃ receptors (e.g, tegaserod, ondansetron, tropisetron, granisetron, dolasetron, mirtazepine, cilansetron);
3. All narcotics (e.g, codeine, morphine, and propoxyphene, either alone or in combination)

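### Gallbladder size is recorded as two uncombined dimensions, the ANCOVA does not adjust for its own baseline, and no analysis set is stated although patients without a gallbladder may enrol

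*Combined protocol and SAP*

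**What the plan says.** Under Quantitative Traits, the paragraph on gallbladder size gives a hormone-driven effect on filling as its reason and then states the question: "We want to determine if there is any difference of baseline and post treatment gallbladder measurements". The scan is fasting 2-D ultrasound before and after treatment. In the sagittal plane, "The image will be captured and the length will be measured". For the second reading, "The probe will then be rotated 90 degrees to obtain the short axis and obtain the greatest dimension in that window". No area, volume or other combination of the two readings is defined, and the question does not mention the treatment arms.

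The Statistical analyses paragraph gives one model for treatment effects: ANCOVA under intention-to-treat principles with four covariates, namely BMI, gender, baseline transit and baseline fecal bile acid excretion. Baseline gallbladder size is not among them, and the paragraph does not say whether the response is the post-treatment value or the change.

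The inclusion table bars prior abdominal surgery with two exceptions: "Abdominal surgery (except appy or choly". The Visit 3 and Visit 7 text says only "Ultrasound measurement can be performed before or after the 24 hour image is obtained" and makes no provision for patients without a gallbladder. The design is "30 IBS-D patients with BAM will be randomized (15/group) in 4-week double-blind, parallel-group trial". Gallbladder size is neither a primary nor a secondary endpoint and does not appear in Table 3.

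**The concern.** Two readings at two visits allow several different tests: length, short-axis dimension, a product, an approximate volume, each as a post-treatment value or as a change. With nothing fixed beforehand, a reader of the result would not know which was chosen or in how many patients.

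Gallbladder size is likely to differ between patients for reasons unrelated to treatment, and the patient's own baseline reading is the natural covariate for removing that variation. The listed covariates do not include it. With about 15 patients per arm, leaving that variation in the error term can cost a good deal of the available sensitivity, and a null result would then say little. The eligibility rule adds a denominator that is not stated.

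**Working it through.** **The plan's own figure.** Table 3 gives SD 6.6 and detectable difference 7.00 for stools per week. 7.00/6.6 = 1.06 SD. A two-sample t-test with 15 per group (28 df, two-sided 0.05) has power 80.1%, and its detectable difference at 80% is 6.99. The stated figure reproduces. There is no gallbladder figure to check.

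**Effect of adjusting for own baseline.** The documents give no gallbladder SD, measurement error or target difference, so all inputs here except 15 per group and alpha are assumptions: a 30% volume difference between arms, equal proportional change in every dimension, independent error e per dimension per visit, SD of baseline log volume 0.30, and SD of true log-volume change 0.15. Take S = ln(length) + ln(short-axis dimension).

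- Effect on S: (2/3) × ln 1.30 = 0.175.
- Variance components at e = 0.10: between patients B = (2/3 × 0.30)² = 0.040; true change G = (2/3 × 0.15)² = 0.010; error E = 2 × 0.10² = 0.020.
- Post-treatment value, unadjusted: B + G + E = 0.070; d = 0.175/0.265 = 0.66.
- Change: G + 2E = 0.050; d = 0.175/0.224 = 0.78.
- ANCOVA on baseline S: B + G + E − B²/(B + E) = 0.070 − 0.0016/0.060 = 0.0433; d = 0.175/0.208 = 0.84.

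Power from the noncentral t (28 df; 27 df for ANCOVA), ignoring the four listed covariates in every column:

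| Baseline SD | Change SD | Error e | Post only | Change | ANCOVA |
|---|---|---|---|---|---|
| 0.30 | 0.15 | 5% | 51% | 90% | 91% |
| 0.30 | 0.15 | 8% | 46% | 69% | 73% |
| 0.30 | 0.15 | 10% | 42% | 54% | 60% |
| 0.15 | 0.15 | 10% | 64% | 54% | 67% |
| 0.50 | 0.15 | 10% | 23% | 54% | 57% |
| 0.30 | 0.30 | 10% | 31% | 37% | 40% |

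In these rows ANCOVA on own baseline beats both alternatives. The gain over post-treatment values runs from 3 to 40 points, and over change from 1 to 13.

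**Would a third diameter help?** For a change score on k dimensions, d = (k/3) ln 1.30 / √[((k/3) × 0.15)² + 2k e²]. Over e = 10% down to 5%, two dimensions give 54% to 90% and three give 68% to 95% (69% against 80% at e = 8%). That gain assumes independent errors. If the two short-axis errors correlate at 0.7 (assumed), 2k e² for k = 3 becomes 2(3 + 2 × 0.7)e² = 8.8e², and three dimensions give 55%, 70% and 91% at 10%, 8% and 5% error, about 1 point better than two. With a change SD of 0.30 and independent errors, the gain is 3 to 6 points (54% to 57% at 5% error, 37% to 43% at 10%).

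An approximate volume from length × width², which assumes a circular cross-section, has relative error √(1 + 4) = 2.24e, against √3 = 1.73e with three separate diameters. It is less precise but usable.

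**Denominator.** The share with a prior cholecystectomy is not given. Detectable standardised difference at 80% power, and power at 1.06 SD, for assumed shares split equally between arms:

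| Share without gallbladder | n | Detectable | Power at 1.06 SD |
|---|---|---|---|
| 0% | 30 | 1.06 SD | 80% |
| 10% | 27 | 1.12 SD | 75% |
| 20% | 24 | 1.20 SD | 70% |
| 30% | 21 | 1.29 SD | 64% |
| 40% | 18 | 1.41 SD | 56% |

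If each patient independently had a 5%, 10% or 20% chance of prior cholecystectomy, the chance that all 30 still have a gallbladder would be 0.95³⁰ = 21%, 0.90³⁰ = 4% or 0.80³⁰ = 0.1%.

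**The case against.** The best defence is that this is an exploratory trait on which no decision in the plan rests. The stated question, about a difference between baseline and post-treatment readings, also points towards analysing change. If change were used, baseline would already be partly accounted for, and in the worked example the gain from ANCOVA is 54% to 60%, not 42% to 60%. That stands, although the plan does not commit to change. Visit 1 also includes a medical history, so a missing gallbladder would normally be known before any scan.

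Three stronger readings are tempting, and the documents do not support them.

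- A reader might infer that the measure is a weak scale because a 30% volume change is only a 9.1% change in length (1.30^(1/3) − 1). But length alone is not the plan, since a short-axis reading is also taken. A cube root by itself also loses no power, because relative error shrinks with it. The advantage of a third diameter rests on independent errors, for which the documents offer no evidence.
- A reader might infer that scans are ordered for patients without a gallbladder. The visit text addresses only the timing of the scan and is silent on these patients.
- A reader might infer that fewer than 30 will be analysable. That is likely, but no cholecystectomy count or rate is given.

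**Conclusion.** The point holds as a minor one. Two dimensions are recorded without a rule for combining them, the stated covariates omit the measure's own baseline, and eligibility allows patients in whom it cannot be taken. The gain from adjusting for own baseline is in a predictable direction, but its size depends on assumed SDs: in the worked case, power rises from 42% to 60% against unadjusted post-treatment values and from 54% to 60% against change.

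The documents do not establish that the two-dimension scale is inadequate. Filling appears only in the rationale, while the question concerns gallbladder measurements in general. Nothing here touches the primary or secondary endpoints or the stated power.

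**What to change.** Add to the analysis text, before unblinding, that gallbladder size is an exploratory outcome defined as one log measure built from the recorded dimensions. This could be log length plus log short-axis dimension, or an approximate log volume with the circular cross-section assumption stated. Compare post-treatment values between arms by ANCOVA with the baseline value of the same measure as a covariate, in patients with a gallbladder in situ, and report n by arm. This uses data already collected and costs a few lines of text.

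A perpendicular short-axis diameter, and from it an ellipsoid volume (π/6 × length × width × height), may be added as a supplementary analysis for patients not yet scanned or with short-axis images stored at both visits. Its precision gain cannot be quantified from the documents. The downside is coverage. This protocol version is dated 15 October 2018 and expects three quarters or more of the patients to have finished by 1 November 2018, which leaves at most 0.25 × 30 = 7.5, about seven patients, still in progress. Image capture is stated only for the sagittal view, so most patients may have only two dimensions. The two-dimension measure should therefore remain the main one.

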Open-label study of the BA sequestrant, Colesevelam, in 12 patients with IBS-D and high fecal bile acid excretion demonstrated biological relevance of increased fecal BA excretion (27).

[figure not shown]

Figure 7. Effects of colesevelam on sequestration of bile acid (methanol extraction of stool released the bile acids showing that increased amounts were bound) and reduced stool form. Colesevelam improved stool consistency, sequestering and inactivating BA (shown by increased BA in stool after methanol extraction).

METHODS

Participants: Eligibility of 30 patients with IBS-D and evidence of BAM. *Through the application of natural language processing and the electronic medical record, we have an established database of ~8000 patients with IBS who reside within ~100 miles, and have been evaluated at Mayo Clinic in Rochester, Minnesota; about ~2000 have been identified with IBS-D.* All participants with IBS-D will be selected by computer-based random selection to be invited to participate. The randomly selected 300 patients with IBS-D will complete a validated bowel disease questionnaire, including Somatic Symptom Checklist [BDQ corresponding to Rome III criteria (58)], IBS quality of life [IBS-QOL (59)], and the Hospital Anxiety and Depression Scale [HAD (60)]. Ethnicity and race information is available in >90% of patients at Mayo Clinic.

Consideration of Sex as a Biological Variable: Scientific premise for inclusion of both genders includes: (i) IBS-D affects both genders; (ii) there is no a priori evidence that mechanisms or pathobiology of IBS-D differs between genders. We shall set up special efforts to recruit males with IBS using REDCAP to identify male patients through the electronic health records (established 17 years ago at Mayo Clinic).

Participants with IBS-D will be screen for BAM 3 ways with either fasting serum alpha C4 or FGF19 taken before 10 am. If C4 \geq 40 ng/mL or FGF19 \leq 80 pg/mL either in the past or at the time of screen, the patient will be included in the trial and subsequently randomized. Also IBS-D with a fecal BA >2000 μ moles/48h either in the past or at the time of screen will be included in the trial or subsequently randomized.

Quantitative Traits

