BA kinetics: Assessment of BA synthesis and fecal excretion (uniquely available in USA at Mayo Clinic) Serum 7α -hydroxy-4-cholesten-3-one (7α -HCO or C4) measures hepatic cholesterol synthesis, and is a validated method for BA malabsorption [BAM (51,52)]. Serum C4 (ref. 53, assay based on ref. 54) is positively correlated with fecal BA excretion [$r_s=0.61$, $p<0.001$ (5)].

Serum fibroblast growth factor 19 (FGF19), a measure of feedback regulation of BA synthesis (54B), will be measured by ELISA (R&D Systems, Minneapolis, MN).

Fecal BA excretion: Using HPLC/tandem mass spectrometry, we adapted a method (55) to measure fecal total and individual BAs. We have previously shown that fecal total BA (5), and **secretory** primary and secondary BAs [chenodeoxycholic (CDCA) and deoxycholic acids (DCA)] are higher in IBS-D, whereas CDCA is decreased and non-secretory lithocholic acid increased in IBS-C (56)].

Short chain fatty acids (SCFAs) in stool by gas chromatography-mass spectrometry (Mayo CTSA ICL Lab) The method is adapted from Tangerman et al. (57) and permits analysis of 8 SCFAs, from C2 to C6, plus an internal standard, 2-ethyl butyric acid using a Thermo Trace GC Ultra Gas Chromatograph (San Jose, CA) fitted with a flame ionization detector (FID). Fecal samples are extracted using acetonitrile and injected without dilution; components were identified according to their retention times compared to standards.

Studies on Sigmoid Mucosal Biopsies: Tight Junction Proteins, Morphology, RNA-Seq. With informed consent, 8 samples will be acquired from the rectum and sigmoid colon and 4 from terminal ileum, for each patient. Biopsies will be immediately preserved in formalin (histopathology), or in a solution of RNAlater (Ambion, Austin, TX), stored at -80°C . RNA extraction will be performed as in the manufacturer's instructions (RNeasy mini kit, Qiagen, Valencia, CA). The quantity and quality of the extracted RNA will be determined by the NanoDrop 2000 spectrophotometer (Thermo Scientific, Wilmington, DE) and the Bioanalyzer 2100 (Agilent Technologies, Inc., Santa Clara, CA). All RINs will be determined using the Agilent Bioanalyzer. RNA-Seq analysis will be conducted as in section C.1.e and as in Camilleri et al. (36). Ileal mRNA of ASBT (SLC10A2) and FXR (NR1H4) in ileal mucosa will be measured by RT-PCR (see C.2.9.i.).

Quantitation of Tight Junction (TJ) Proteins in Sigmoid Mucosa Using Real-Time PCR.

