In Depth Proteomics of colonic mucosal biopsies in duplicate by a label-free LC-MS/MS method (see letter of support from [name] Ph.D., Proteomics Core, Mayo).

Extraction and separation: Proteins from the biopsy will be extracted in SDS buffer containing protease inhibitors using a bead beater to disrupt tissue. Extracted proteins will be run on a gel, proteins separated by size, segmented, and in-gel trypsin digested to obtain peptides to compare across samples.

Liquid chromatography is used to load peptide sample onto a C8 cartridge, which is then placed in-line with a C18 analytical column. Peptides are sorted by ionic strength using a mobile phase gradient of acidic low to high organic solvent, eluted off the column, captured into mass spectrometer (MS) via electrospray ionization, followed by data dependent ms/ms data for peak identification. D. We also have access to single reaction monitoring (SRM) mass spectrometry on QExactive and triple quad instruments in the Proteomics Core for more accurate quantification of proteins if necessary.

Data analysis from high resolution MS will use MaxQuant, a quantitative proteomics software to compare high resolution MS data. Database searching within MaxQuant assigns amino acid sequence to peptides and assembles peptide information back to proteins. Quantified values of proteins between groups are compared.

Biological Samples Collected

1. **Venous Blood Sample** (fasting) will be collected for **serum FGF19 and C4. Venous blood DNA will be stored for future genetic studies.**
2. **Fecal Sample for Fecal Organic Acids:** Gas chromatography-mass spectrometry for SCFA in stool and HPLC tandem MS for total and individual fecal BAs. Samples will now be a random stool sample without a required dietary change unless they have not had a qualifying diagnosis of BAM as noted in the Research Plan below. Samples will then be processed for total fat (routine van de Kamer method at Mayo Medical Laboratory), **total BAs**, and **primary and secondary BAs** [by LC/MS as previously described from our lab (56)], and **SCFA by GC-MS**
3. Additional **stool** and rectosigmoid **mucosa samples** will be **stored for future microbiome studies.**

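### The primary-endpoint ANCOVA omits each endpoint's own pretreatment diary baseline, which is already collected, and adjusts instead for a fecal bile acid covariate whose stool specimen is not named

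*Combined protocol and SAP*

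**What the plan says.** - **Model.** Under Statistical analyses, treatment effects are compared by intention to treat using ANCOVA with BMI, gender, "baseline colonic transit and baseline fecal BA excretion as covariates". No specimen, unit or time window is given for the fecal term. The text does not say whether the outcome is the on-treatment value or the change from baseline.
- **Primary endpoints.** Bowel movements per week and stool consistency on the BSFS, both from daily diaries. A 7-day pretreatment diary is returned by Visit 5 (Visits 2 and 5 both list it).
- **Fecal BA, assay and scale.** The BA kinetics section gives the assay with no collection period: "Fecal BA excretion: Using HPLC/tandem mass spectrometry, we adapted a method (55) to measure fecal total and individual BAs". The entry thresholds for total fecal BA, the Specific Aim in the Research Plan and Table 3 all express it per 48 h.
- **Fecal BA, baseline specimen.** Biological Samples Collected, item 2: "Samples will now be a random stool sample without a required dietary change unless they have not had a qualifying diagnosis of BAM". Visit 1 reserves the 48-hour stool test for patients with no previous qualifying result, and their random stool follows at least a week later. Visit 5 lists a single random stool. Under Participants, a qualifying C4 or FGF19 suffices for entry: "either in the past or at the time of screen, the patient will be included in the trial and subsequently randomized".
- **On treatment.** Experimental procedures list "fecal bile acid and fat excretion and fasting serum C4 and FGF-19" at baseline and at the end of 28 days. The TREATMENT paragraph mentions a fat diet with stool collections after the other tests. It then mentions a separate Visit 6 kit, with no diet, to be returned before sigmoidoscopy. A note suspends the treatment diary during a high fat diet. Sigmoidoscopy is optional.
- **Power.** The claim of about 80% is made to "detect clinically relevant effect sizes in stool frequency and form". Table 3 also has rows for fecal BA per 48 h and for "Fecal Fat g/24h".

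**The concern.** In a parallel-group trial of 15 per arm with a diary outcome, the patient's own pretreatment value is usually the most informative covariate available. The plan collects it and leaves it out of the model, while spending a degree of freedom on a laboratory covariate it has not defined.

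The fecal term has two readings. As 48-h excretion, it may be missing for patients who qualified earlier on C4 or FGF19, and historical for those who qualified on a past stool. As the random-stool value, it exists on schedule for everyone. The readings put different covariates into the primary model, and the choice falls to the analyst. At stake are precision and analyst discretion in a small trial with an interim analysis planned.

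Two further matters follow from the same sampling change. The timed-collection rows of Table 3 no longer match a random stool. The on-treatment text also leaves open which collection supplies "Secondary endpoints: 1. Quantitative total fecal BAs", and which diary days count if the diary is paused.

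**Working it through.** **1. Reproduce Table 3.** Inputs: 15 per group, two-sided alpha 0.05, 80% power, SDs from Table 3. The detectable difference Δ solves P(T > t(0.975, df)) = 0.80, where T is noncentral t with noncentrality Δ / (SD × √(2/15)). With df = 28 this gives Δ = 1.0598 × SD.

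| Row | SD | 1.0598 × SD | Stated |
|---|---|---|---|
| Stools/week | 6.6 | 6.99 | 7.00 |
| BSFS | 1.0 | 1.06 | 1.06 |
| Fecal BA, µmol/48h | 2456 | 2603 | 2650 |
| Fecal fat, g/24h | 3.1 | 3.29 | 3.30 |

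All four rows reproduce. At the stated differences the fecal rows have 81.4% and 80.3% power.

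**2. Value of the diary baseline.** Residual SD = SD × √(1 − r²), where r is the correlation between the pretreatment and on-treatment diary values. The documents give no r, so 0.3, 0.5 and 0.7 are assumed. The other covariates are taken as uninformative. If the diary baseline replaces fecal BA, residual df = 30 − 6 = 24 (intercept, treatment, BMI, gender, transit, own baseline), the same as the planned model. With df = 24, Δ = 1.0663 × residual SD. If both are kept, df = 23 and the multiplier is 1.0683.

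| r | √(1 − r²) | Stools/week, df 24 (df 23) | BSFS, df 24 (df 23) |
|---|---|---|---|
| 0 | 1.000 | 7.04 (7.05) | 1.066 (1.068) |
| 0.3 | 0.954 | 6.71 (6.73) | 1.017 (1.019) |
| 0.5 | 0.866 | 6.09 (6.11) | 0.923 (0.925) |
| 0.7 | 0.714 | 5.03 (5.04) | 0.761 (0.763) |

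The proportional reduction, 1 − √(1 − r²), is about 5%, 13% and 29%, and it does not depend on the SD. Keeping the fecal covariate as well costs 0.01 to 0.02 stools/week.

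**3. If the Table 3 SDs were change-score SDs.** With equal variances at the two times, a change has variance 2σ²(1 − r) and the ANCOVA residual has σ²(1 − r²). The SD ratio is √((1 + r)/2) = 0.806, 0.866, 0.922. The detectable difference would then be 7.04 × these = 5.67, 6.09, 6.49 stools/week: still a gain, but of a different size.

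**4. Which baseline stool exists in whom.**

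| Patient | 48-h stool | Random stool |
|---|---|---|
| Past qualifying C4 or FGF19 only | none scheduled | yes |
| Past qualifying stool test | historical only | yes |
| No past qualifying result | at screening | yes, at least one week later |

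Only the random stool is scheduled in every patient. It can give concentrations and proportions. Nothing in the plan turns it into µmol/48h or g/24h.

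**The case against.** The strongest reply is that the current text nearly answers the specimen question: the assay section attaches no collection period, the sampling section names the random stool for total and individual BAs, and every patient is scheduled to give one. That largely stands, so the unnamed specimen is a secondary point.

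A second reply is that the gains rest on assumed correlations, and that Table 3 does not say whether its SDs are baseline, on-treatment or change values. That stands too. Means of 15.1 stools/week and 4.4 on a 1–7 scale read more like levels than changes, but this is inference. The direction of the gain survives either way; the absolute figures are conditional.

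A third reply is that the outcome may be intended as change from baseline. The plan does not say so. Adding the baseline covariate gives the same treatment estimate for either form of outcome.

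A reader might infer more than the documents support:

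- *That the comparison is biased or primary power is lost.* Randomisation protects the comparison under either reading of the covariate, and the power claim concerns stool frequency and form.
- *That Table 3's fecal rows are wrong.* Their arithmetic reproduces; only the scale is at issue. Fecal fat is not a listed endpoint.
- *That declining the second sigmoidoscopy loses the fecal BA endpoints.* No passage assigns the Visit 6 kit to those endpoints. Item 3 of the sampling list also stores additional stool for microbiome work.
- *That the on-treatment lines flatly contradict each other.* The separate kit can be read as a second collection. The text needs reconciling but does not prove a conflict.

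**Conclusion.** The point holds in this form: the primary model leaves out the two pretreatment diary values that most directly predict its outcomes, and adding them needs no new data. Under assumed correlations of 0.3 to 0.7, and taking Table 3's SDs as unadjusted on-treatment SDs, detectable differences fall from about 7.0 to between 6.7 and 5.0 stools/week, and from 1.07 to between 1.02 and 0.76 BSFS points. The cost is at most one degree of freedom.

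The undefined fecal BA covariate is a lesser matter of analyst choice. Its effect on precision is unknown, because the plan does not say how many patients enter on a past C4 or FGF19. The fecal BA and fat rows of Table 3 describe timed collections and do not carry over to random stools unless a timed collection is kept.

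**What to change.** 1. Adjust bowel movements/week and BSFS each for its own 7-day pretreatment diary value.
2. Either drop the fecal BA covariate or define it as one prespecified measure from the pretreatment random stool in every patient, such as total BA concentration. Do not mix it with 48-h or historical values.
3. Mark the per-48-h and per-24-h rows of Table 3 as not applying to random-stool sampling, unless a timed collection is kept.
4. Reconcile item 2 of Biological Samples Collected, Experimental procedures and the TREATMENT paragraph on on-treatment stool collection, diet and diary pause. State which collection supplies the fecal BA endpoints, when it is returned if the optional sigmoidoscopy is declined, and which diary days enter the primary endpoints.

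Cost: no new sample or visit for items 1 and 2. A concentration is a less direct measure than timed excretion, and the fecal detectable differences cannot be restated because no random-stool SD is given. Timing is tight. This version is dated 15 October 2018, and the plan expects at least 75% of participants complete by 1 November 2018, with an interim analysis. The amendment should therefore be dated before that analysis and made while assignment is blinded.
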